shoulder ROM measurements of the patients were performed using a standard manual goniometer. Measurements were made in the supine position, and active forward flexion (FF), abduction (US), internal rotation (IR), and external rotation (ER) were measured. The IR and ER measurements were made with the shoulder abducted at 90°. The PPT measurements were obtained over the middle deltoid, upper trapezius, infraspinatus, and tibialis anterior muscles using a 1 cm diameter probe from an electronic digital display algometer (Commander Echo® Algometer, JTECH Medical, Midvale, UT, USA). Measurements were taken directly on the skin and vertically, and the patient was instructed to stop when the feeling of pressure first turned into a feeling of pain and discomfort. Three measurements were taken from each region, and the average of the last two measurements was recorded. The PPT values were expressed as kilograms per square centimeter (kg/cm²). A low PPT value represents a decrease in the pain threshold and, therefore, increased sensitivity. A 5-point Likert scale was used to evaluate the patients' overall satisfaction with the treatment (1= extremely dissatisfied, 2= dissatisfied, 3=neutral, 4= satisfied, and 5= extremely satisfied).

The patients' compliance with the exercise program was queried at the 4th and 12th weeks after the injection. The patients were asked to choose between "Never did," "I did it occasionally," and "I did it regularly." Finally, they were asked how much they used the paracetamol (500 mg) and naproxen (750 mg) that had been sent home with them after the injection at the 1st, 4th, and 12th weeks. The total amount of drug used was recorded.

Statistical Analyses

The sample size required for the research was calculated via a website (<http://statulator.com/SampleSize/ss2M.html>). In a previous study, the Minimal Clinically Important Difference (MCID) value for SPADI ranged from 8 to 13 points (2). We established our research hypothesis that the clinical results of SSNB at the level of the spinoglenoid notch would not be non-inferior to SSNB at the level of the suprascapular notch. Accordingly, when the non-inferiority margin is -9 and the standard deviation is 15.3; With 80% power and type 1 error 0.05, 36 patients in each group should be recruited. Assuming a 10% dropout rate, 40 patients were planned for each group.

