The collected data were statistically analyzed using IBM SPSS ver. 22.0 (IBM Corp., Armonk, NY, USA). All analyses were performed according to the "intention to treat" principle, and the missing data were completed using the single imputation method. The Shapiro-Wilk test, as well as histograms and QQ plots, were used to test whether the data were normally distributed. Analysis results were presented as mean \pm standard deviation for numerical data and as numbers and percentages for categorical data. For numerical data, the differences between groups were compared using the independent samples t-test or the Mann-Whitney U test. Categorical data were analyzed using chi-square tests or Fisher's exact test. In addition, the differences (Δ) between the baseline value of the outcome measures and the values at the follow-up time points were calculated and included in the intergroup comparison. The Friedmann test was used for intragroup comparisons of the changes in outcome measures from baseline to follow-up times. The post hoc Dunn-Bonferroni test was then used for

pairwise comparisons of follow-up times. A P value less than 0.05 was considered statistically significant.

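### The trial is framed and sized for non-inferiority with a margin of -9 SPADI points, but the analysis plan only tests for a difference and never uses the margin

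*Combined protocol and SAP*

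**What the plan says.** **Design.** The sample-size paragraph of Statistical Analyses gives the hypothesis that results of the block "at the level of the spinoglenoid notch would not be non-inferior to SSNB at the level of the suprascapular notch". Read literally this is a double negative; the margin that follows shows that non-inferiority was meant. The inputs are introduced by "when the non-inferiority margin is -9 and the standard deviation is 15.3", then "With 80% power and type 1 error 0.05, 36 patients in each group should be recruited" and "Assuming a 10% dropout rate, 40 patients were planned for each group". The unit of the margin is not printed, but the preceding sentence concerns the MCID of SPADI.

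**Analysis.** The next paragraph lists the between-group methods: "For numerical data, the differences between groups were compared using the independent samples t-test or the Mann-Whitney U test" and "Categorical data were analyzed using chi-square tests", with Fisher's exact test as the alternative. The same comparison is also made on "the differences (Δ) between the baseline value of the outcome measures and the values at the follow-up time points". Friedman and Dunn-Bonferroni tests are for changes within a group. Everything is read at P<0.05. The population is intention to treat, and "the missing data were completed using the single imputation method".

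**Outcome.** Outcome Measures makes SPADI the primary outcome, measured at baseline and weeks 1, 4 and 12, with higher scores worse. Week 12 is singled out only in the definition of treatment success (a fall of at least 18 points in total SPADI).

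The margin appears once, in the sample-size sentence. No confidence interval, shifted test or rule for concluding non-inferiority appears anywhere.

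**The concern.** A non-inferiority claim needs evidence that excludes a deficit as large as the margin. A test of no difference does not supply that. A significant t-test favouring the spinoglenoid block would imply non-inferiority, and a significant result against it would practically always fail the margin too. The gap is the non-significant result, which is the most likely one if the blocks are equal or nearly so: P>0.05 does not show that the deficit is under 9 points. If the Mann-Whitney test is the one used, it yields no mean difference to set against -9 at all.

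An interval could be derived from the reported means and SDs, but the plan leaves open its confidence level, the visit (three candidates) and the scale (follow-up score or change from baseline; the document does not say which the SD of 15.3 describes). Three visits by two scales already give six candidate primary contrasts, so the verdict could turn on choices made after the data are seen.

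**Working it through.** **Inputs.** Margin 9, SD 15.3, power 80%, type 1 error 0.05, 36 per group, 10% dropout and 40 per group are all from the sample-size paragraph. Two things are not printed: the sidedness of the 0.05, and the assumed true difference, taken as 0.

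**1. Reproduce the plan's figure.** n per group = 2·SD²·(z₁₋α + z₀.₈₀)² / margin².
- One-sided 0.05: 2·15.3²·(1.645 + 0.842)² / 9² = 35.7, so 36, as stated. 36/0.9 = 40, as stated.
- One-sided 0.025: 2·15.3²·(1.960 + 0.842)² / 9² = 45.4, so 46.

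The plan's 36 therefore corresponds to one-sided 0.05. A one-sided 0.05 test to detect 9 points uses the same formula, so this identifies the alpha; it is the stated hypothesis and margin that make the design non-inferiority. A two-sided 0.05 test for 9 points would need 46, so conventional two-sided tests are not what 36 was sized for.

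**2. Compare the two rules.** SE = 15.3·√(2/n). Half-widths use the t distribution on 2n-2 degrees of freedom. Write the difference so that positive means the spinoglenoid block is worse.

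| | 36 per group | 40 per group |
|---|---|---|
| SE | 3.606 | 3.421 |
| 90% half-width | 6.01 | 5.69 |
| 95% half-width (smallest significant difference) | 7.19 | 6.81 |
| Observed deficit must be below, 90% CI (9 - half-width) | 2.99 | 3.31 |
| Observed deficit must be below, 95% CI | 1.81 | 2.19 |

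At 36 per group, an observed deficit between 2.99 and 7.19 gives P>0.05 and fails the margin. Just significant against the spinoglenoid block means a deficit of 7.19, where the 90% upper limit is 7.19 + 6.01 = 13.2, well past 9.

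**3. How often this matters.** Normal data with a common SD of 15.3; the 3-point deficit is an illustrative assumption, not a figure from the document.

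| Probability | True deficit 0 | True deficit 3 |
|---|---|---|
| P>0.05 and 90% CI fails margin, n = 36 | 0.179 | 0.372 |
| The same as a share of non-significant trials, n = 36 | 0.188 | 0.428 |
| P>0.05 and 90% CI fails margin, n = 40 | 0.143 | 0.326 |
| Significant in favour of spinoglenoid, n = 36 | 0.025 | 0.0027 |
| 90% CI passes, 95% CI fails, n = 36 | 0.10 | 0.13 |

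**4. If non-significance were taken as non-inferiority.** With a true deficit of 9, P>0.05 occurs with probability 0.308 at 36 per group and 0.262 at 40, against the 0.05 used for sizing.

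**5. Power of a margin-based rule at true difference 0** (noncentral t). 90% CI: 0.796 at 36, 0.832 at 40. 95% CI: 0.692 and 0.738.

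**The case against.** The omission itself is hard to dispute; the fair objections concern its size.

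- The 18% and 37% are not wrong conclusions. With a true deficit of 0 or 3 the block really is within the margin, and a correct 90% CI analysis misses non-inferiority in 20.4% of trials anyway when the blocks are equal (17.9% non-significant plus 2.5% significantly adverse). This stands: they measure how often the two rules disagree.
- The 31% needs a reading that the plan never states. This stands too; it is a conditional risk.
- With imputation under intention to treat, the nominal sample is 40 per group, which lowers the figures to 14%, 33% and 26%. Imputed values do not carry full information, so the truth lies between the two columns, and the conclusion is the same in both.
- The sign of the margin does not alter the decision. Improvement as spinoglenoid minus suprascapular, or raw score as suprascapular minus spinoglenoid, both mean no more than 9 points worse. Accepted; stating it is a matter of clarity.
- The success definition and the use of change scores point towards change at week 12. They do, but neither passage ties the margin to that contrast.
- An interval can be derived from the summary statistics. It can, but that is not a decision rule.

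**Conclusion.** The concern holds and must be fixed, because it affects the primary outcome and the trial's central claim. Followed as written, the analysis leaves the stated hypothesis unanswered whenever the result is non-significant, which is 95% of trials if the blocks are equal. Among those non-significant trials, about 19% would fail the margin on a 90% CI, and about 43% if the true deficit is 3 points. The choice of confidence level alone would change the verdict in about 10% to 13% of trials.

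These figures assume SD 15.3, normal data and 36 evaluable per group. The one-sided 0.05 is inferred from the sample size. The absence of a margin-based rule depends on none of these assumptions.

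**What to change.** State one primary decision rule:

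- **Estimate.** The between-group mean difference in total SPADI with a two-sided 90% CI, which matches the one-sided 0.05 implied by 36 per group.
- **Scale and visit.** Name one of each. The scale should be the one that the SD of 15.3 describes, which only the authors can say. Week 12 is the natural visit, but it is a choice and should be stated as one.
- **Rule.** With positive meaning that spinoglenoid is worse, declare non-inferiority only if the upper limit is below +9. State the order of subtraction that gives the printed -9.
- **Method.** Use this interval whatever the Shapiro-Wilk result, with a bootstrap interval as a sensitivity analysis if skewness is a worry. Keep the t-test and Mann-Whitney P values as descriptive.
- **Wording.** Correct the hypothesis to say that the spinoglenoid block would be non-inferior.
- **Status.** Study Design and Patients gives the study period as June 2021 to August 2022. Unless a rule dated before the data were seen exists, label the non-inferiority result post hoc.

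The cost is a few lines of text and one interval from data already collected. Power is about 80% at 36 evaluable per group (83% only if all 40 are observed). The downside is that a 90% CI is less strict than a 95% CI. If a 95% CI is preferred, restate power as about 69% at 36 (74% if all 40 are observed); 80% would have needed about 46 evaluable per group (47 on the t distribution). A late rule cannot be presented as pre-specified.

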[name]

NCT04938037 UNIQUE PROTOCOL ID: 2021/353

05.05.2020

Comparison of Spinoglenoid Versus Suprascapular Notch Approaches for Ultrasound-Guided Distal Suprascapular Nerve Blocks for Shoulder Pain: A Prospective Randomized Trial

Study Design and Patients

The present study was conducted in a prospective, randomized, double-blind fashion at a tertiary-care university hospital in Kayseri, Turkey, from June 2021 to August 2022. The Consolidated Standards of Reporting Trials (CONSORT) guideline was used as the reference for the standardization of the data reported in this study. Ethical approval for the study was obtained from the Erciyes University Clinical Research Ethics Committee (approval date: May 05, 2020; approval number: 2021/353). The study was also registered at ClinicalTrials.gov (NCT04938037). The research adhered to the Ethical Principles for Medical Research Involving Human Subjects outlined in the World Medical Association's Declaration of Helsinki, as revised in 2013. A written informed consent form approved by the ethics committee was signed by each participant who agreed to participate in the study.

All patients over the age of 18 who had chronic shoulder pain of any specific etiology (duration >3 months), had a visual analog scale (VAS) score above 4 despite conservative treatment, and gave informed written consent were screened for eligibility for the study. Exclusion criteria were previous fractures or surgery around the shoulder, receipt of any injections to the affected shoulder in the last 3 months, chronic pain due to other diseases such as malignancy, cervical radiculopathy, hemiplegia, or uncontrolled diabetes or hypertension, coagulopathies, local infection over the shoulder region, or allergy to local anesthetics.

The clinical diagnosis of chronic shoulder pain for each included patient was determined by physical examination and radiologic imaging technique (magnetic resonance imaging [MRI] or ultrasound [US]).

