Patients were randomized into two groups: Group 1 received SSNB at the spinoglenoid notch level, while Group 2 received SSNB at the suprascapular notch level. Stratified randomization was performed in four blocks based on age and gender. Group allocations were made (using sealed envelopes) by our medical secretary. The assigned numbers were presented to the physician at the time the procedure was performed. The patients and the physician assessing the outcomes were blinded to the group assignments, but the physician who performed the injections could not be blinded.

Procedures

All injections were administered by a single experienced physician specializing in musculoskeletal injections who used the linear transducer (LA3-16AD) of the Samsung HM70A Plus US device (Seoul, South Korea). The same injection solutions were prepared for both groups and consisted of 1 mL of methylprednisolone acetate (40 mg/mL) and 5 mL of 0.5% bupivacaine for the SSNB.

For SSNB at the level of the spinoglenoid notch, the patients were positioned on a stretcher in the lateral decubitus position between the US device and the physician. The patient's hand on the side of the injection was placed on the contralateral shoulder. The transducer was positioned on the glenohumeral joint, parallel to the inferior border of the spina scapula, and then shifted medially to visualize the spinoglenoid notch. After sterile prep, a 20G 3.5-inch needle was advanced, using an in-plane technique, into the spinoglenoid notch. A lateral-medial needle insertion was used so that the intended target of the final needle tip was at the medial wall of the spinoglenoid notch.

For SSNB at the level of the suprascapular notch, the technique described by Harmon et al.(1) was used. In brief, the patient was positioned seated between the physician and the US equipment. The patient's injection-side hand was placed on the shoulder on the opposite side. To view the suprascapular notch, the transducer was positioned above the acromion, parallel to the spina scapula, and then gently adjusted medially. After sterile prep, a 20G 3.5-inch needle was advanced into the suprascapular notch.

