One week after the injection, all patients received a prescribed exercise regimen to be performed in their own homes. The exercise routine encompassed self-stretching, joint mobility exercises, and strength-building activities. A designated physical therapist demonstrated the exercises to each patient individually, and an exercise booklet was provided to assist them.

Finally, the patients were advised to use paracetamol (500 mg) and/or naproxen (750 mg), if necessary. They were asked not to take analgesics at or 1 day before the follow-up points, as it could affect the clinical outcome measures.

Outcome Measures

All patients were evaluated for primary and secondary outcome measures before injection (baseline) and at 1, 4, and 12 weeks after injection by an investigator blinded to the injections. The primary outcome measure of the study was the Shoulder Pain and Disability Index (SPADI), while the secondary outcome measures were visual analog scale (VAS) scores, active range of motion of the shoulder (ROM), pressure pain thresholds (PPT), and treatment satisfaction. All adverse events that occurred during the procedure and at a follow-up visit were recorded.

Primary outcome measure: The Shoulder Pain and Disability Index is a shoulder-specific index consisting of 13 items that assess shoulder pain and disability on two different scales. Each item is scored between 0 and 10, and the resulting score is converted into a 100-point scale separately for pain, disability, and total score. Increased SPADI scores indicate an increase in patients' shoulder-related pain and disability. Patients with a reduction in the total SPADI score of 18 points or more from baseline to week 12 (the last follow-up) were considered treatment successes. (2). The SPADI has been shown to be valid and reliable in Turkish (3).

Secondary outcome measures: The VAS (0–10 range) was evaluated in each patient for night and activity. An additional VAS assessment was performed 1 h after the injection. Active

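### SPADI is compared between arms by unadjusted tests on both raw and change scores, with no rule for which decides; one baseline-adjusted ANCOVA would be more precise and would give one answer.

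*Combined protocol and SAP*

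**What the plan says.** - **Between-group tests (Statistical Analyses).** For numerical outcomes, "the differences between groups were compared using the independent samples t-test or the Mann-Whitney U test". A second comparison is then added: for each outcome and visit, changes since baseline "were calculated and included in the intergroup comparison". No ANCOVA, regression or mixed model appears anywhere.
- **Randomisation (Study Design and Patients).** "Stratified randomization was performed in four blocks based on age and gender". No analysis uses age or gender. SPADI is not a stratification factor.
- **Primary outcome (Outcome Measures).** SPADI is primary and is measured at baseline and weeks 1, 4 and 12, as pain, disability and total scores. The text does not say which score or week decides, or whether the follow-up value or the change does. The only rule tied to one time point is the responder definition: patients whose total score falls by at least 18 points "from baseline to week 12 (the last follow-up) were considered treatment successes". It is not named as the deciding test.
- **Sample size (Statistical Analyses).** "when the non-inferiority margin is -9 and the standard deviation is 15.3", 80% power and a type 1 error of 0.05 give 36 per arm, raised to 40 for 10% dropout. The plan does not say whether 15.3 is the SD of the score or of its change.

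**The concern.** A test on raw follow-up scores ignores baseline SPADI. A test on change scores uses baseline, but with its slope fixed at 1. ANCOVA estimates that slope from the data and in large samples is at least as precise as either. The age and gender strata go unused as well. If they are prognostic, the unadjusted tests are conservative; the documents do not show whether they are.

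The second problem is the open choice. The two mean differences differ by exactly the observed baseline difference in SPADI between the arms. In a trial of this size that difference can be large relative to a 9-point margin, so one estimate may support non-inferiority while the other does not. The plan gives no rule for choosing, and a reader could not tell whether the reported result was the one intended.

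**Working it through.** **Inputs from the plan:** margin 9 points, SD 15.3, 36 evaluable patients per arm, 80% power, alpha 0.05.

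**Assumptions:** the baseline-to-follow-up correlation r is not in the documents, so r = 0.3, 0.5 and 0.7 are used. Baseline and follow-up SDs are taken as equal, and the normal approximation is used.

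**1. The plan's own figure.** With one-sided alpha 0.05, n = 2 × (15.3 × (1.645 + 0.842) / 9)² = 35.7, so 36 per arm; 36 / 0.9 = 40. One-sided 0.025 would need 46, so the stated size rests on one-sided 0.05, which is used below.

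**2. Relative variance.** With the raw-score variance set to 1, change scores have 2(1 − r) and ANCOVA has 1 − r². ANCOVA relative to change is therefore (1 + r)/2.
- Against raw scores, ANCOVA variance is lower by r²: 9%, 25% and 49%.
- Against change scores, it is lower by (1 − r)/2: 35%, 25% and 15%.

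**3. Power at 36 per arm.** Power = Φ(9 / (SD × √(2/36)) − 1.645). Both readings of 15.3 are shown. If it is the SD of change, the raw-score SD is 15.3 / √(2(1 − r)) = 12.9, 15.3 and 19.8.

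| r | 15.3 = raw-score SD: raw / change / ANCOVA | 15.3 = SD of change: raw / change / ANCOVA |
|---|---|---|
| 0.3 | 80% / 68% / 83% | 90% / 80% / 93% |
| 0.5 | 80% / 80% / 89% | 80% / 80% / 89% |
| 0.7 | 80% / 94% / 97% | 61% / 80% / 86% |

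From the unrounded values, the gain over the better unadjusted test runs from 0.927 − 0.905 (2 points) to 0.892 − 0.803 (9 points).

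**4. Chance baseline imbalance.** The 95% range is 1.96 × SD × √(2/36). With SD 15.3 this is ±7.1 points; with 12.9 and 19.8 it is ±6.0 and ±9.1.

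**5. Disagreement between the two tests.** The raw and change estimators have correlation √((1 − r)/2) = 0.592, 0.500 and 0.387. With no true difference, the probability that exactly one shows non-inferiority (1,000,000 simulated trials) is:
- 26%, 22% and 20% if 15.3 is the raw-score SD;
- 18%, 22% and 34% if it is the SD of change.

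**6. Error if either test may decide.** At a true deficit of 9 points, each test passes with probability 0.05, so P(either) = 0.10 − P(both). From the bivariate normal with the correlations in step 5 this is 8.5%, 8.8% and 9.1%, the same under both readings.

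**The case against.** The strongest reply is that both tests are valid under randomisation and the sample size reproduces, so ANCOVA is only a preference for efficiency. On validity that is right, and no bias is alleged here.

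The size of the gain also depends on equal SDs. Eligibility requires a VAS score above 4, which may narrow the baseline spread. If the baseline SD is 0.7 times the follow-up SD, the change-score variance is 1 + 0.49 − 1.4r relative to raw. With 15.3 as the raw-score SD, power for raw/change/ANCOVA becomes 80/78/83%, 80/88/89% and 80/97/97%. The gain over the better test is then 3, 1 and 0 points, disagreement falls to about 15% to 18%, and the either-test error to 7.7% to 8.0%. This stands as a limit on magnitude. It does not change the direction: ANCOVA is still never worse in large samples, and which unadjusted test is the better one depends on an r that nobody can read from the plan.

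Three further points are fair.
- The plan never says that success on either test suffices, so the error figure is conditional.
- The Statistical Analyses section describes only difference tests at P < 0.05, so the verdicts modelled above presuppose a comparison with the margin that the plan does not set out. The fix has to supply it.
- Naming either existing comparison would also remove the raw-versus-change choice. ANCOVA by itself leaves the score and week open, so these must be fixed too.

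The benefit of adjusting for age and gender cannot be quantified from the documents. The phrase about four blocks is also unclear: it could mean four strata or blocks of four.

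**Conclusion.** The concern holds. SPADI is compared twice between arms without adjustment, the stratification factors are unused, and no comparison is named as deciding.

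With equal SDs and r from 0.3 to 0.7, the gain from ANCOVA over the better unadjusted test is 2 to 9 points of power, or about 1 to 8 when t-tests are used and three covariates are estimated. With a narrower baseline spread it may be only 0 to 3. The open choice matters at least as much: under equal SDs, 18% to 34% of trials with no true difference would give conflicting verdicts against the margin.

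The precision ordering holds for any r between 0 and 1 in large samples. Its size rests on r, the SD ratio and the meaning of 15.3, none of which the documents give. This should be changed, but it does not invalidate the trial.

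**What to change.** - Make the primary comparison one ANCOVA, or an equivalent mixed model, of week-12 total SPADI on arm, with baseline SPADI, age and gender as covariates. Week 12 and the total score are proposed because the responder definition already uses them.
- Report the adjusted mean difference with its confidence interval and judge non-inferiority by that interval against the 9-point margin.
- If residuals are clearly non-normal, keep the same adjusted difference with a bootstrap interval. A Mann-Whitney test gives no mean difference to set against a margin in SPADI points.
- Use the same baseline-adjusted model for VAS, range of motion and pressure pain thresholds, and label the raw and change-score tests as descriptive.
- State whether 15.3 is the SD of the score or of the change, and what the four blocks are.

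**Cost.** No new data are needed: baseline SPADI, age and gender are already collected. The document describes a study run from June 2021 to August 2022. If the data have been analysed, the model cannot be presented as pre-specified and should be reported as a disclosed post hoc re-analysis beside the original results.

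### Within-arm Friedman and Dunn-Bonferroni P values, and a one-arm treatment-success share, cannot be attributed to the block because there is no sham or untreated arm; report them as descriptive

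*Combined protocol and SAP*

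**What the plan says.** All references are to the combined protocol and SAP.

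- **Arms (Study Design and Patients).** "Group 1 received SSNB at the spinoglenoid notch level, while Group 2 received SSNB at the suprascapular notch level". No sham, placebo or untreated group is described. Under Procedures, the injectate is the same in both arms and "consisted of 1 mL of methylprednisolone acetate (40 mg/mL) and 5 mL of 0.5% bupivacaine for the SSNB".
- **Entry (Study Design and Patients).** Patients have had shoulder pain for more than 3 months and "had a visual analog scale (VAS) score above 4 despite conservative treatment".
- **Co-treatments (Procedures).** From one week after the injection, every patient has a home exercise programme. Paracetamol and naproxen are allowed as needed, and patients are asked to avoid them on the day of a visit and the day before.
- **Within-arm analysis (Statistical Analyses).** "The Friedmann test was used for intragroup comparisons of the changes in outcome measures from baseline to follow-up times". Next, "The post hoc Dunn-Bonferroni test was then used for" pairs of visits. One rule covers every test: "A P value less than 0.05 was considered statistically significant". Nothing marks the within-arm tests as descriptive.
- **Responder label (Outcome Measures).** Patients whose total SPADI falls by "18 points or more from baseline to week 12 (the last follow-up) were considered treatment successes".
- **Between-arm analysis (Statistical Analyses).** The hypothesis and sample size concern non-inferiority of one site to the other, with a 9-point margin. The named between-arm tests are the t-test or Mann-Whitney U test, applied also to change from baseline, and chi-square or Fisher tests for categorical data. No confidence interval against the margin is mentioned.

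**The concern.** A test of change from baseline asks whether scores moved, not why. With no comparison group outside the two blocks, the movement in an arm combines any effect of the injection with natural course, exercise, analgesic use and any regression to the mean. The design cannot separate these parts. The same holds for the proportion of one arm that meets the 18-point cut-off, although the label treatment success attributes the fall to treatment.

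At stake is the interpretation. A report that follows the plan could show a non-significant between-arm P value beside two significant within-arm P values. A reader could take that pattern to mean that both approaches work and are similar, and it supports neither statement. Even a properly shown non-inferiority result between two active arms would leave open whether either block is effective, so the within-arm results are where such a claim would most naturally be sought.

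**Working it through.** **1. The plan's own figure.** Inputs from Statistical Analyses: margin 9, SD 15.3, power 80%, type 1 error 0.05.

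n per arm = 2 × [15.3 × (1.645 + 0.842) / 9]² = 35.7, so 36. With 10% dropout, 36 / 0.9 = 40.

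Both stated numbers reproduce, with 0.05 taken as one-sided (one-sided 0.025 would need 46). The trial is sized for the between-arm question only.

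**2. How often the planned within-arm test is significant with no block effect.** The documents give neither the size of any non-specific improvement nor the correlation between visits, so both are assumptions shown as ranges:

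- 40 per arm and four visits (baseline, weeks 1, 4 and 12);
- normal scores with SD 15.3 at each visit (the plan does not say whether 15.3 is an SD of scores or of change);
- equal between-visit correlation of 0.3 to 0.7;
- the same improvement in both arms, half reached by week 1, 80% by week 4 and all by week 12.

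Friedman statistic: 12n / [k(k+1)] × Σ(mean rank − (k+1)/2)², with k = 4 and n = 40, referred to chi-square on 3 degrees of freedom. Simulated rates are rounded and carry an error of about two percentage points.

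| Shared improvement in SPADI | P<0.05 in one arm | P<0.05 in both arms |
|---|---|---|
| 5 points | about 23-52% | about 6-26% |
| 10 points | about 78-99% | about 58-98% |

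With 36 per arm, the one-arm range at 10 points is 73-98%.

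**3. Adding the post hoc step.** For each pair of visits, z = difference in mean ranks / √[k(k+1)/(6n)], judged at 0.05/6 because four visits give six pairs. Requiring significance from baseline to both week 4 and week 12, in both arms, gives about 9-64% of trials at 10 points and under 2% at 5 points.

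**4. Share labelled a treatment success with no block effect.** Share = 1 − Φ[(18 − m) / SD of change], where m is the mean improvement and SD of change = 15.3 × √[2(1 − correlation)]. This SD is 18.1, 15.3 and 11.9 at correlations 0.3, 0.5 and 0.7.

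- m = 0: 16%, 12% and 6%.
- m = 5: 24%, 20% and 14%.
- m = 10: 33%, 30% and 25%.

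**5. The randomised comparison.** With the same improvement in both arms, the between-arm t-test on change to week 12 stays near its nominal level: 4.1-6.0% across the settings run with 36 per arm. Shared influences cancel on average.

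**6. Regression to the mean from the entry rule.** Expected VAS fall = (1 − ρ) × SD × φ(a) / [1 − Φ(a)], with a = (4 − mean) / SD. For an assumed VAS mean of 5-6, SD 2 and test-retest correlation ρ of 0.6-0.8, this is 0.12-0.41 points. It is small, and it reaches SPADI only through the correlation of SPADI with VAS.

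**The case against.** The strongest reply is that the misuse is predicted rather than found. The only hypothesis concerns one site against the other, the sample size rests on it, between-group tests come first in the analysis text, and change from baseline is taken into the between-group comparison. Responder proportions can already be compared with the planned chi-square or Fisher tests. Exercise compliance and analgesic use are recorded. All of this stands, and it limits the point to what the within-arm results may be taken to mean.

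A reader might infer more than the documents support:

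- *That the plan claims the blocks are effective.* It does not. Only the treatment-success label leans that way.
- *That significance in both arms at weeks 4 and 12 is very likely whatever the block does.* The 9-64% at 10 points and under 2% at 5 points do not support this. A paired t-test makes it look likelier than the planned test does: with 36 per arm, a 10-point improvement and an SD of change of 15.3, it is significant in 97% of arms, against 87% for Friedman.
- *That the steroid is a rival explanation.* It is part of the injectate as defined. It blurs nerve-block effect with drug effect, but it is not outside the treatment given.
- *That entry on high pain explains the improvement.* On the values assumed it contributes at most about 0.4 VAS points.
- *That significance in both arms would be false if the sites do not differ.* Two equally effective sites would also give it. The design cannot tell the two situations apart.

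None of this makes a within-arm P value evidence that a block works.

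**Conclusion.** The point holds as a matter of interpretation and reporting. The plan gives within-arm tests the same significance rule as the randomised comparison and does not label them descriptive, in a design that cannot attribute within-arm change to the block.

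The size depends on a non-specific improvement that the documents do not quantify. Under the stated assumptions, spurious-looking significance in both arms is common at 10 points and uncommon to moderate at 5. The randomised comparison, sample size, endpoint and allocation are unaffected. The change is worth making because it alters what the report can properly conclude at almost no cost.

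**What to change.** - Replace the within-arm Friedman and Dunn-Bonferroni P values with mean change and confidence interval per arm and visit, labelled descriptive.
- Compare the 18-point responder proportion between arms only. Renaming the outcome is optional, since it leaves the cut-off and the analysis unchanged.
- Base the conclusion on the between-arm difference in SPADI with its confidence interval against the 9-point margin. State the interval's level; the planned sample size corresponds to one-sided 0.05.
- Add a sentence that the design does not test whether either block is effective.

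Cost: wording in the analysis plan and report, and fewer tests to run. No new data, patients or visits are needed. The downside is that the report can no longer say that each block significantly improved outcomes.
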